9. DESIGN

A multicentre, analytical, observational study of two cohorts. One cohort will be constituted by the patients to whom a TAVI will be implanted, and that meet non-invasive diagnostic criteria of TTR amyloidosis (capturing of radiotracer in grades 2 and 3 and absence of monoclonal gammopathy the PE of urine or serum). The other cohort will be constituted by patients whose TAVI implants do not meet the diagnostic criteria for TTR amyloidosis.

A clinical and echocardiographic follow-up will be done in all patients for two years.

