 1. DATA COLLECTION
 2. DATA MANAGEMENT
 3. DATA CONFIDENTIALITY
14. PRACTICAL USE OF THE RESULTS
15. ETHICS
16. ANNEX
 1. ECHOCARDIOGRAPHY PROTOCOL
 2. SCINTIGRAPHY PROTOCOL
 3. DECLARATION OF HELSINKI

1. STUDY SUMMARY

Study title and code	Prognostic impact of cardiac amyloidosis in patients with severe aortic stenosis who underwent percutaneous implantation of an aortic prosthesis (AMY-TAVI)
Study type and design	Observational analytical of multicenter prospective cohorts.
Number and characteristics of patients	321 patients to whom a TAVI has been implanted by severe degenerative AoS.
Study duration	Recruitment period: All the consecutive patients to whom a non-invasive diagnostic study of amyloidosis (scintigraphy with tecnecio ⁹⁹ pyrophosphate and electrophoresis of proteins in the blood) and to whom a percutaneous aortic prosthesis for severe aortic stenosis has been implanted. Follow-up period: clinical and echocardiographic monitoring will be done before discharge, in consultation at three, six, twelve, and twenty-four months. Inclusion: 1 year Follow-up: 2 years Data analysis: 6 months Total: 3 years and 6 months
Events	Main event: cardiovascular events (cardiovascular death, stroke, heart attack), death from any cause, readmission for cardiac insufficiency, pacemaker implantation, functional assessment
Participating countries and centers	Various Spanish and international centers will be invited to participate.

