9.2. INCLUSION CRITERIA

- Replacement of the aortic valve with a percutaneous prosthesis by severe aortic stenosis after evaluation by the Heart Team.

- Ability to understand and sign informed consent.

- Do not meet any of the exclusion criteria.

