11. PATIENTS FOLLOW-UPS

11.1 INITIAL PATIENT ASSESSMENT

An initial inclusion visit will assess whether the patient is a candidate who meets the inclusion criteria and none of the exclusion ones. After being informed, if they accept, the informed consent must be signed. The following data must be recorded:

- **Clinical parameters:** age, sex, height, weight, body mass index, body surface, cardiovascular risk factors, medication intake, background interests, history of heart disease, presence of ischemic heart disease, cerebrovascular accident, peripheral artery disease, chronic obstructive pulmonary disease, symptoms (angina, syncope, dyspnea according to grades of the NYHA, other symptoms), blood pressure, heart rate, evidence of heart failure, assessment of functional class by means of 6MT and fragility assessment.
- **Analytical parameters:** hematocrit, NT-proBNP, Troponin I, electrolytes, C-reactive protein, creatinine, glomerular filtrate.
- **Protein electrophoresis:** Rating presence of the monoclonal component
- **Scintigraphy with TC⁹⁹:** Assessment of values of tracer uptake.
- **Device parameters:** Type of prosthesis, dimensions, expandable/ self-expanding ball, post-dilatation.
- **ECG parameters:** Rhythm, PR duration, pacemakers, implantable cardioverter defibrillator, QRS duration.

- The 6 minute-test: All patients in the study will have a test of 6 minutes before implantation and 6 months follow-up, according to the protocol after a TAVI, in order to carry out an objective functional assessment of the functional capacity. The distance covered will be determined, the variation of oxygen saturation by means of non-invasive pulse oximetry before and after the test and the appearance of symptoms with the effort according to the Borg scale.

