12. WORK PLAN

	Basal	3 months	6 months	1 year	2 years
Clinical history	X				
Informed Consent	X				
Clinical assessment	X	X	X	X	X
ECG	X		X	X	X
Analysis ¹	X		X	X	X
Protein electrophoresis	X				
Scintigraphy with tecnecio ⁹⁹	X				
Echocardiogram with strain	X		X	X	X
The 6-minute test	X		X		
Events assessment		X	X	X	X

1: includes: hemoglobin, hematocrit, lipid profile, NT-proBNP, TnT, electrolytes, C-reactive protein, creatinine, and glomerular filtrate.

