13. DATA MANAGEMENT

13.1. DATA COLLECTION:

All the patients will receive standard treatment according to clinical practice guidelines and consensus in force. The criteria for inclusion/ exclusion will be assessed in all of them to confirm the feasibility of entering the study, which will be offered, explained, and then the appropriate informed consent collected. Subsequently, following the predefined protocol, a number of epidemiological variables, clinical, laboratory, electrocardiographic, echocardiographic, functionals, scintigraphy with Tc⁹⁹basals of the patient will be collected before discharge. All previously detailed. All the data will be collected in the Data Collection Logbook (DCL), which is designed to register all the data required in the protocol and collected by the researcher. The data on the DCL will be coded. The data entry will be done by the researcher or the person assigned by them, and then that data will be transferred to the database of the study. The researcher or the appointed person in their team commits to completing the DCL on each visit made by the participant. All data corrections in the DCL will be made by the researcher or the person assigned in their team in accordance with the instructions given. After the last visit from the participant and the closure of the DCL, the researcher must attest, by signing the DCL, the authenticity of the data collected in the DCL, the coherence between the data in the DCL and the data contained in the source document.

13.2 DATA CONFIDENTIALITY:

All documents and information provided to the researchers by the promoter regarding the study are confidential. Both the researcher and their collaborators undertake to use the information provided only within the framework of this study to carry out this protocol. This commitment remains as long as the confidential information has not been made public by the promoter. The protocol delivered to the researcher can be used by them or their collaborators to obtain informed consent from the participants entering the study. It should not be disclosed to third parties without the written consent of the promoter. This information will be treated in accordance with the rules of professional secrecy. The screening list must be completed when the researcher verifies that the participant can enter the study after confirming their record and medical history.

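### The comparator is defined as a remainder and completed testing is not an inclusion criterion, so patients with a missed test, or with grade 2–3 uptake plus a monoclonal protein, can be counted as amyloid-free

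*Combined protocol and SAP*

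**What the plan says.** The documents describe the study population and the two cohorts in several places, and these do not fully agree.

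- **Study summary (section 1, study duration).** Recruitment is "All the consecutive patients to whom a non-invasive diagnostic study of amyloidosis" has been done, scintigraphy and electrophoresis both being named, and who have had a TAVI.
- **Section 9.2.** There are three criteria: "Replacement of the aortic valve with a percutaneous prosthesis by severe aortic stenosis after evaluation by the Heart Team", ability to consent, and "Do not meet any of the exclusion criteria". Neither test appears. Section 9.3 does not exclude a patient who lacks one.
- **Section 9.** The amyloid cohort needs uptake of grade 2 or 3 and no monoclonal gammopathy. The comparator is everyone else: "The other cohort will be constituted by patients whose TAVI implants do not meet the diagnostic criteria for TTR amyloidosis".
- **Section 8.1.** The primary contrast is between patients diagnosed by both tests and patients without amyloidosis.
- **Section 11.1.** After eligibility and consent, "The following data must be recorded", and the list includes electrophoresis and scintigraphy ("Assessment of values of tracer uptake").
- **Section 12.** "Protein electrophoresis" and scintigraphy are both marked in the baseline column.
- **Section 13.1.** Consent comes first. "Subsequently, following the predefined protocol, a number of epidemiological variables, clinical, laboratory, electrocardiographic, echocardiographic" and scintigraphy data follow, with collection due before discharge.

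No section says how a missed, incomplete or uninterpretable test is classified.

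**The concern.** Test status is the exposure in the primary comparison. Not meeting the TTR criteria is a wider category than not having amyloidosis, and the gap holds two kinds of patient.

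The first is a patient enrolled under section 9.2 whose scan or electrophoresis is never completed. That patient's amyloid status is unknown, but the literal rule puts the patient, and any death, in the comparator.

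The second is a fully tested patient with grade 2–3 uptake and a monoclonal protein. This patient fails the TTR criteria and so joins the comparator, although section 4 attributes false-positive scans almost exclusively to AL amyloidosis.

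A site that screens against section 9.2 and a site that follows the summary could enrol different patients, and a reader of the results could not separate tested-negative from not tested.

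**Working it through.** **Step 1. Apply the wording of section 9 to each possible patient.**

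| Test results | Cohort under section 9, read literally | Amyloid status |
|---|---|---|
| Both done, grade 2–3, no monoclonal protein | Amyloid | TTR amyloidosis |
| Both done, scan below grade 2 | Comparator | TTR criteria tested and not met |
| Both done, grade 2–3, monoclonal protein | Comparator | Per section 4, likely AL amyloidosis |
| Grade 2–3, electrophoresis missing | Comparator | Unresolved |
| No scan | Comparator | Unknown unless a monoclonal protein already rules out the TTR criteria |

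The last three rows do not fit the comparator intended in section 8.1. The last two would not be recruited under the summary, but section 9.2 lets them in.

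**Step 2. Inputs and the plan's own figure.** The sample-size subsection of section 10 gives 15% prevalence, two-year mortality of 40% and 17%, alpha 5%, power 80%, 306 patients, and 321 after 5% losses. It words the 17% as mortality after TAVI; I read it as comparator mortality. It names no formula and does not state sidedness; I take two-sided.

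- Hazard ratio = ln(0.60)/ln(0.83) = 2.742, whose log is 1.0085.
- Schoenfeld events = (1.960 + 0.842)² / (0.15 × 0.85 × 1.0085²) = 60.5, so 61.
- Pooled risk = 0.15 × 0.40 + 0.85 × 0.17 = 0.2045, and 61/0.2045 gives 299 patients, 2.3% below 306.
- 306 × 1.05 = 321.3, which matches 321.

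The two-proportion formula gives about 213 (247 with continuity correction), so the event-based route is the closer match.

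**Step 3. Amyloid patients untested at random.** 321 × 0.15 gives 48 amyloid patients, leaving 273. Expected deaths are 48 × 0.40 = 19.2 and 273 × 0.17 = 46.41. The risk ratio is 0.40/0.17 = 2.35.

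- 10% untested: 4.8 patients with 1.92 deaths move. Comparator risk = 48.33/277.8 = 17.4%; ratio 2.30.
- 20% untested: 9.6 patients with 3.84 deaths move. Comparator risk = 50.25/282.6 = 17.8%; ratio 2.25.

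**Step 4. Amyloid deaths before a scan at two weeks, constant hazard.** Early deaths = 48 × (1 − 0.60^(0.5/24)) = 0.51. Amyloid risk = 18.69/47.49 = 39.4%; comparator risk = 46.92/273.51 = 17.2%; ratio 2.29.

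**Step 5. Direction.** Take 306 patients with 10% of all patients untested (30.6) and placed in the comparator beside 306 × 0.85 × 0.9 = 234.09 tested patients. If m is the untested patients' mortality, comparator risk = (39.80 + 30.6m)/264.69.

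| m | Comparator risk | Risk difference (points) |
|---|---|---|
| 12% | 16.4% | 23.6 |
| 17% | 17.0% | 23.0 |
| 30% | 18.5% | 21.5 |

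The contrast shrinks only when m exceeds 17%.

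**Step 6. Power (Schoenfeld, 306 patients, 15% prevalence among the untested).** With complete testing it is 81.3%. With 10% untested and placed in the comparator, the amyloid cohort falls from 45.9 to 41.3, the hazard ratio to 2.67 and power to 75.7%. With 20% the figures are 36.7, 2.61 and 69.3%.

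Leaving the 10% out instead gives 275.4 × 0.2045 = 56.3 events; √(56.3 × 0.1275) × 1.0085 − 1.96 = 0.742, a power of 77.1%. So most of the loss comes from the missing tests, and only 1.4 points from putting the untested in the comparator.

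**The case against.** The strongest reply is that the protocol, read as a whole, expects everyone to be tested. The summary recruits patients who had the work-up, section 11.1 makes both results mandatory, section 12 schedules both at baseline, and section 13.1 closes collection before discharge. On that reading, failing the criteria means tested and found not to meet them. Two routes to a missing test are also narrowed: section 9.3 excludes in-hospital death from a procedural complication, and section 11.3 treats transfer to another health area as withdrawal.

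Most of this stands, and it limits the size of the problem. It does not supply a rule. Sections 11.1 and 13.1 are data-collection instructions that take effect after consent; they are neither an eligibility condition nor a classification for the patient in whom collection fails. The reply also does not reach the patient with grade 2–3 uptake and a monoclonal protein, who is misplaced even when testing is complete.

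Three stronger readings are tempting, and the documents do not support them:

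- **That untested patients are assigned to the comparator as stated policy, biasing the contrast toward no effect.** No section says so, and Step 5 shows that the direction depends on their mortality.
- **That scans may come one or three months after TAVI.** The same arithmetic would then give ratios of 2.24 and 2.01, but collection before discharge leaves these delays without a basis.
- **That patients are scanned on clinical suspicion.** The summary says consecutive patients, and the scan is a scheduled baseline procedure.

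**Conclusion.** The defect is one of definition. Completed testing is missing from section 9.2, the comparator is a remainder, and incomplete tests have no rule. As worded, the comparator can take in patients of unknown status and does take in tracer-positive patients with a monoclonal protein.

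The effect of missed tests on the primary contrast is small on the planning figures: a risk ratio of 2.35 becomes 2.30–2.25 with 10–20% of amyloid patients untested, or 2.29 with scanning at two weeks. This rests on assumptions: the untested share and the two-week delay (the documents give neither), a constant hazard in the delay calculation, and 17% as comparator mortality. Above 17% among the untested is plausible if tests are missed through frailty or early death, but that too is an assumption. The number of patients with grade 2–3 uptake and a monoclonal protein cannot be estimated from the documents, so I put no size on that part.

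The change is worth making because it concerns the exposure variable and costs little.

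**What to change.** - **Section 9.2:** carry over the summary's requirement, so that inclusion is of consecutive TAVI patients with scintigraphy and electrophoresis both completed and interpretable. Count recruitment toward 321 in such patients; this is what protects power.
- **Section 9:** define the comparator as patients with both tests completed and scintigraphy below grade 2.
- **Reporting:** show two groups outside the primary contrast, each with its number and deaths listed: consented patients lacking either test, and patients with grade 2–3 uptake plus a monoclonal protein. The second is a deliberate change to the comparison and should be stated as one.
- **Data collection:** record the scan date. Use delayed entry, with follow-up starting at the scan, only for a scan done after TAVI.

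The cost is a few lines of protocol text and one date variable. The downside is that a few enrolled patients leave the primary comparison.

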9.1. POPULATION

Elderly patients, enlisted in the hospitalization area or from outpatients clinics that meet the following requirements will be included in the study: diagnosis of severe aortic stenosis by conventional echocardiographic criteria (maximum speed >4m/s, medium transvalvular gradient >40mmHg, area <1cm²).

9.2. INCLUSION CRITERIA

- Replacement of the aortic valve with a percutaneous prosthesis by severe aortic stenosis after evaluation by the Heart Team.

- Ability to understand and sign informed consent.

- Do not meet any of the exclusion criteria.

9.3. EXCLUSION CRITERIA

- Death as a result of a complication of the procedure during hospitalization.

- An associated mitral valve requiring intervention

- TAVI implant valve-in-valve.

- Does not sign informed consent.

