7. HYPOTHESIS

Amyloidosis is a disease which coexists in a high percentage of patients referred for TAVI by severe aortic stenosis; the pathophysiological mechanisms of this relationship have a negative impact on prognosis.

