8. OBJECTIVES

8.1 PRIMARY OBJECTIVE

A multicentre prospective study of cohorts consisting of two cohorts from patients who have been implanted with percutaneous aortic prosthesis as treatment for the severe degenerative aortic stenosis and compare the overall mortality and that for

cardiovascular and admissions for heart failure in the 2-year follow-up of patients diagnosed with amyloidosis (by GT99 and EFP) versus those that do not have it.

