14. PRACTICAL USE OF THE RESULTS

The progressive aging of our population carries an increasing prevalence of degenerative aortic valve stenosis in our country, constituting a public health problem

of crucial importance. There is scientific evidence that amyloidosis is an underdiagnosed disease in clinical practice, which coexists simultaneously in a large number of patients suffering from aortic stenosis, and that could overshadow the prognosis. To determine the prevalence and prognostic impact of amyloidosis referred for percutaneous implantation of an aortic prosthesis is important in order to understand the interrelationship of both diseases. This information will guide us to take the appropriate measures in need of a screening and the early treatment that will allow optimizing the resources available.

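### Excluding in-hospital deaths from procedural complications removes primary-outcome deaths by cause, so the mortality compared is neither all-cause mortality after TAVI nor mortality among patients discharged alive

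*Combined protocol and SAP*

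**What the plan says.** Section 9.3 of the combined protocol and SAP gives as its first exclusion criterion "Death as a result of a complication of the procedure during hospitalization". Section 9.2 makes freedom from every exclusion criterion a condition of inclusion, so the rule is binding.

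Section 8.1 (primary objective) sets out to "compare the overall mortality", together with cardiovascular mortality and heart-failure admissions, over two years between patients with and without amyloidosis. The population there is "patients who have been implanted with percutaneous aortic prosthesis". Section 1 lists "death from any cause" among the main events, with no exception for procedural deaths.

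Section 10.1 (statistical analysis) plans relative risks, hazard ratios, Kaplan-Meier curves, the log-rank test and Cox regression, without declaring a time origin. The sample-size section assumes 15% prevalence of amyloidosis and two-year mortality of 17% after TAVI and 40% with amyloidosis. It arrives at 306 patients, raised to 321 for 5% losses.

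**The concern.** An event that belongs to the primary outcome is also a ground for exclusion. The rule depends on what happens after implantation and on the judged cause. A patient who dies in hospital of a procedural complication leaves the study. A patient who dies in hospital of something else stays and counts as a death.

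At stake are the absolute two-year mortality in each cohort, the size of the relative risk (RR) and hazard ratio (HR), and the statement of which patients these figures describe. No section asks for the excluded deaths to be counted, so a reader of the results could not tell how many were removed or from which cohort.

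**Working it through.** **1. What the rule keeps and removes**

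| Death | Rule in section 9.3 | All-cause from implantation | All-cause from discharge |
|---|---|---|---|
| In hospital, procedural | removed | counted | not in cohort |
| In hospital, other cause | counted | counted | not in cohort |
| After discharge | counted | counted | counted |

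The rule matches neither of the two usual definitions.

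**2. The plan's own figure.** The inputs come from the sample-size section: risks pA = 0.40 (amyloid) and pN = 0.17 (taken as non-amyloid), allocation 15:85, alpha 0.05 (two-sided assumed) and power 80%. The method is not named. With the Schoenfeld log-rank formula:

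- HR = ln(0.60)/ln(0.83) = 2.74
- Events = (1.960 + 0.842)² / (0.15 × 0.85 × (ln 2.74)²) = 60.5, rounded up to 61
- Average risk = 0.15 × 0.40 + 0.85 × 0.17 = 0.2045
- N = 60.5/0.2045 ≈ 296, or 61/0.2045 ≈ 299 with whole events, against the stated 306
- Losses: 306 × 1.05 = 321.3, against the stated 321

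This approximately reproduces the plan. A pooled two-proportion formula does not (211, or 244 with continuity correction).

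**3. Illustration of the exclusion.** The documents give no procedural death rate, so the rates q below are assumptions. It is also assumed that 17% and 40% include procedural deaths and that the rule removes all of them. Then:

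- Risk after exclusion = (p − q)/(1 − q)
- RR = ratio of these risks
- HR = ln(1 − risk A)/ln(1 − risk N), assuming proportional hazards
- Deaths removed = 306 × (0.15 qA + 0.85 qN)

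Without exclusion, 306 × 0.2045 = 62.6 deaths are expected.

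| qA / qN | Risk A | Risk N | RR | HR | Deaths removed |
|---|---|---|---|---|---|
| none | 0.400 | 0.170 | 2.35 | 2.74 | 0 |
| 1% / 1% | 0.394 | 0.162 | 2.44 | 2.84 | 3.1 |
| 3% / 3% | 0.381 | 0.144 | 2.64 | 3.08 | 9.2 |
| 5% / 1% | 0.368 | 0.162 | 2.28 | 2.61 | 4.9 |

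At 3%/3%, whole-sample mortality falls from 20.5% to (0.2045 − 0.03)/0.97 = 18.0%. Equal rates raise both ratios. A sufficiently higher rate in the amyloid cohort lowers them.

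**4. Against sampling error.** Cohort sizes are 306 × 0.15 = 45.9 and 306 × 0.85 = 260.1. The standard error of ln RR is √(0.60/(0.40 × 45.9) + 0.83/(0.17 × 260.1)) = 0.227. The approximate 95% interval for RR 2.35 is therefore 2.353 × exp(±1.96 × 0.227) = 1.51 to 3.67. Every RR in the table lies well inside it.

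**5. When patients enter.** Sections 1, 8.1 and 9.2, the device data in section 11.1 and the baseline collection before discharge in section 13.1 point to enrolment after implantation. Against that, section 9 says "One cohort will be constituted by the patients to whom a TAVI will be implanted", section 11.1 has a 6-minute test before implantation, section 11.2 puts that test at the basal visit, and the work plan in section 12 puts consent and scintigraphy there too. The weight favours enrolment after implantation, but the text does not settle it.

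**The case against.** The strongest defence is that patients are enrolled after implantation, so the criterion largely states who could not be enrolled. The future tense in section 9 may be no more than the style of a prospective protocol, and the pre-implantation walk test may be routine work-up. Much of this stands. Under that reading, the rule itself removes only deaths between enrolment and discharge, fewer than the table assumes. It does not rescue the wording: a cohort of patients discharged alive would exclude every in-hospital death whatever its cause, and no discharge time origin is declared.

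Two further points stand. A discharge landmark would not undo the shift in RR, because it leaves out the same procedural deaths; it corrects what the estimate is said to describe. And mortality among patients discharged alive is a legitimate target if it is declared.

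That the rule applies equally to both cohorts is a weaker defence. Step 3 shows that equal removal still changes the ratios.

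**Conclusion.** The point holds and should be fixed, but it does not overturn the comparison. As written, the plan removes primary-outcome deaths by cause and declares no estimand that fits. Absolute mortality after TAVI is understated whenever such a death occurs. The size and direction of the effect on RR and HR cannot be determined from the documents. The illustrated RR range of 2.28 to 2.64 around 2.35 rests on assumed procedural death rates, on 17% being the non-amyloid risk, and on 17% and 40% including procedural deaths.

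A reader might infer more than this, and the documents do not support it:

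- **That the exclusion inflates, or hides, the prognostic effect.** The scenarios go both ways, and none removes the association.
- **That the shifts are larger because 17% is the overall TAVI rate.** The non-amyloid risk would then be (0.17 − 0.15 × 0.40)/0.85 = 12.9% and the HR 3.69, but the Schoenfeld size would be about 213 to 218, far from 306.
- **That the study samples the wrong population because it asks about referred patients.** Section 8.1 names implanted patients. In section 7, "patients referred for TAVI by severe aortic stenosis" belongs to the clause on coexistence of the two diseases, and section 14, with "prognostic impact of amyloidosis referred for percutaneous implantation of an aortic prosthesis", is rationale. Recruiting consecutive patients (section 1) is compatible with having exclusion criteria.

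**What to change.** Delete the cause-based exclusion in section 9.3 and declare time zero in section 10.1.

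- **If amyloid testing and consent precede implantation:** start at implantation, count every death from then on, and use an all-cause discharge landmark as a sensitivity analysis.
- **If enrolment follows implantation:** use an all-cause discharge landmark as time zero and limit the conclusion to patients discharged alive. Report in-hospital deaths by cause, and by cohort where amyloid status is known. This makes the estimate describe what it measures; it does not restore the excluded deaths.

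In either case, state in the sample-size section whether 17% and 40% include in-hospital procedural deaths. As a secondary matter, reconcile sections 1, 8.1, 9, 9.2, 11.1, 11.2, 12 and 13.1 on when patients enter.

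The cost is wording plus a few extra records. Amyloid status may be unknown for patients who die before scanning or consent, so the count by cohort may be incomplete. The price is either a narrower conclusion or some purely technical deaths in the outcome.
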